4.5 Statistical analysis

Data will be analyzed and reported based on established methods in the literature.¹⁸ Statistical significance will be set at 95% confidence level for all tests ($p < 0.05$). Receiver-operating curves will be utilized to assess sensitivity and specificity of

HemeChip in comparison to HPLC as the standard test. Sensitivity will be calculated as $\# \text{ true positives} / (\# \text{ true positives} + \# \text{ false negatives})$ and specificity will be calculated as $\# \text{ true negatives} / (\# \text{ true negatives} + \# \text{ false positives})$. Positive predictive value (PPV) will be calculated as $\# \text{ true positives} / (\# \text{ true positives} + \# \text{ false positives})$ and negative predictive value (NPV) will be calculated as $\# \text{ true negatives} / (\# \text{ true negatives} + \# \text{ false negatives})$.

5 Dissemination of results

Study results will be disseminated at a clinical meeting in the Department of Child Health at Case Western Reserve University, published in peer-reviewed scientific journals and presented at relevant scientific conferences.

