1. BACKGROUND

1.1 Introduction

Sickle cell disease (SCD) is a group of inherited disorders of haemoglobin (Hb) synthesis, first described in the medical literature by James Herrick in 1910. Each year about 300,000 infants are born with SCD, including more than 200,000 cases in sub-Saharan Africa alone.¹ In Nigeria, alone, there are over 150,000 of these children born annually and it is estimated that between 50-90% of these children die before their fifth birthday.² Overall, in the region, 6% of all childhood mortality in children less than 5 years of age is due to SCD complications and infections. Vaso occlusive crisis and anemia are serious complications of SCD, with infection often being the major cause of hospitalizations, crisis and death.

SCD is caused by a point mutation in the sixth codon of the beta globin chain that produces normal Hb (HbA). This substitution of hydrophilic glutamic acid with hydrophobic valine produces sickle Hb (HbS), which is abnormally polymerized at low oxygen conditions causing sickling. Abnormal polymerization of HbS affects red cell membrane properties, shape, and density, and subsequent critical changes in inflammatory cell and endothelial cell function.³ The clinical consequences of SCD include painful crises, widespread organ damage, and early mortality.

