1.3 Relevance and Innovation

HemeChip diagnostic system offers an original and innovative solution, leveraging a novel engineering approach, to point of care (POC) diagnosis of SCD. HemeChip

separates haemoglobin protein types in a miniscule volume of blood (1 μ L) on a piece of cellulose acetate paper that is housed in a micro-engineered chip with a controlled environment and electric field. Differences in Hb mobilities allow separation to occur within the cellulose acetate paper. A micro-engineered design and multiple layer lamination approach are utilized in fabricating the HemeChip. The design allows rapid manual assembly and results are available within a few minutes of performing the test. HemeChip can also integrate with a mobile user interface (e.g. iPhone, iPod), which shows the test result quantitatively and objectively on the screen. HemeChip can be used by anyone after a short (30 minute) training, eliminating the need for highly skilled personnel.

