4.4 Sample size estimate

Sample size is based on the known prevalence of SCD in Nigeria (SCD prevalence of 2.39% and a carrier rate of about 23%)¹⁹, using the following formula and a 95% confidence interval.¹⁷

1. Specify clinically acceptable values for the width of 95% confidence interval (CI), sensitivity (SN), specificity (SP), and the disease prevalence (P).
2. Calculate the number of patients with disease, defined as the sum of true positive cases (TP) and false negative cases (FN) using:

$$TP + FN = Z_{\alpha/2}^2 \frac{SN(1 - SN)}{W^2}$$

3. Calculate the sample size required to obtain the desired sensitivity as:

$$N1 = \frac{TP + FN}{P}$$

4. Calculate the number of patients without disease, defined as the sum of true negative cases (TN) and false positive cases (FP) using:

$$TN + FP = Z_{\alpha/2}^2 \frac{SP(1 - SP)}{W^2}$$

5. Calculate the sample size required to obtain the desired specificity as:

$$N2 = \frac{TN + FP}{P}$$

Where $Z_{\alpha/2}$ is a statistical constant having a value of 1.96 for 95% CI.

6. Select the required sample size as the greater of N1 and N2.

The calculations made for the HemeChip test sample size are summarized in Table 1 below:

Prevalence estimate	P	0.024
Width of the 95% CI: 10%	W	0.10
Sensitivity expected: 98%	SN	0.97
Specificity expected: 98%	SP	0.97
Statistical constant, 1.96 for 95% CI	Zalpha	1.96
Number with disease, True Positive + False Negative	TP+FN	11
Sample size required for sensitivity	N1	468
Number without disease, False Positive + True Negative	FP+TN	11
Sample size required for specificity	N2	11
FINAL SAMPLE SIZE (greater of N1 and N2)		468

Total maximum enrollment of 5,000 patients, age 6 weeks to 60 months identified through CAPIBD.

Procedure

The CAPIBD medical officer will introduce the study and ask if parent/caregiver is willing to participate. If yes, signed informed consent will be obtained and the subject assigned a unique identification number through CAPIBD. The clinical research assistant (CRA) assigned to the study will complete a questionnaire including demographic data and family information, and perform a heel or finger prick to obtain a blood sample for HemeChip and HPLC (page 12).

HemeChip Test

- a. Finger-stick or heel-stick blood sample (20 μ L) is mixed with deionized water for red blood cell lysis and the mixture allowed to set for 3 minutes.
- b. 65 μ L of a buffer solution is used to wet the paper inside the HemeChip.

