- c. A disposable metal applicator is used to stamp 1 μ L of the mixture onto the paper strip inside the HemeChip through the sample application port.
- d. 185 μ L of the buffer solution is pipetted into two buffer chambers through buffer loading inlets on the HemeChip.
- e. The HemeChip is loaded into the reader and the power supply in the reader turned on. The test runs for five minutes and diagnosis is obtained on a computer connected to the reader.
- f. Data is stored on computer and results delivered by fax delivery and secured email to a dedicated port for the attention of study PI.
- g. Study CRA contacts caregivers of screen-positive children via phone and all who screen positive will be referred to the local SCD clinic for follow up care.

HPLC Test

- a. All blood samples collected via heel or finger prick on dot-blot paper will be shipped to the IFAIN lab in Abuja on a monthly basis.

- b. HPLC confirmatory results will be obtained from the IFAIN lab on a monthly basis.
- c. Study CRA contacts caregivers of screen-positive babies via phone following confirmatory results.
- d. All subjects with abnormal HPLC results will be enrolled in the pediatric sickle cell clinic, for parental education, penicillin prophylaxis, pneumococcal vaccination, malaria prevention, fever and pain management protocol, splenic palpation and contact with SCD team.

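### Does the plan leave open which HemeChip result counts as positive, so that sensitivity and specificity could be read off a tuned ROC curve?

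*Combined protocol and SAP*

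**What the plan says.** The primary objective (Section 2.1) is the sensitivity and specificity of HemeChip against HPLC. Section 4.5 states "Receiver-operating curves will be utilized to assess sensitivity and specificity of" HemeChip with HPLC as the standard, then gives the usual formulas for sensitivity, specificity, PPV and NPV from true and false positives and negatives. It names no variable for the curve, no cut-off and no rule for choosing one.

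Three other places bear on what a positive result is.

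- **Test output.** Under Procedure, HemeChip Test, item e, "diagnosis is obtained on a computer connected to the reader". Section 1.3 adds that HemeChip can be linked to a mobile interface "which shows the test result quantitatively and objectively on the screen".
- **Use of the result.** Item g says that "all who screen positive will be referred to the local SCD clinic for follow up care". Under HPLC Test, samples are shipped and results returned monthly, the results are called confirmatory, and "All subjects with abnormal HPLC results will be enrolled in the pediatric sickle cell clinic". Neither the screening term nor the HPLC term is defined.
- **Disease.** Section 1.1 says "Sickle cell disease (SCD) is a group of inherited disorders of haemoglobin (Hb) synthesis", and no list of Hb types follows. Section 4.4 takes the SCD prevalence of 2.39% as its input and quotes the carrier rate of about 23% separately.

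**The concern.** Sensitivity and specificity need one rule that sorts each child's HemeChip result into positive or negative. A ROC curve moves the cut and so produces a series of pairs, whereas the formulas in Sections 4.4 and 4.5 need one fixed call. With the variable, the cut and its timing all unstated, a reader may fear that the cut will be picked once HPLC is known. In a validation study with about 11 expected SCD cases at the planned size, that would flatter sensitivity noticeably.

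A second worry is the carriers. They outnumber SCD cases by almost ten to one (23 / 2.39 = 9.6), so whether a carrier result counts as positive moves specificity and PPV a great deal.

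**Working it through.** **1. Which disease does Section 4.4 use?** Inputs from its table: Z = 1.96, SN = 0.97 (the value cell; the label reads 98%), W = 0.10.

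- Cases needed: 1.96² × 0.97 × 0.03 / 0.10² = 11.18, printed as 11.
- With P = 0.0239: 11.18 / 0.0239 = 467.7, printed as 468. With the rounded 0.024 the result is 465.8.
- With carriers counted as diseased, P = 0.0239 + 0.23 = 0.2539 and N1 = 11.18 / 0.2539 = 44.0.

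The printed 468 is reproduced only with SCD as the disease and carriers outside it.

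**2. Which HemeChip result fits the expected specificity?** Keep disease as SCD and suppose an error-free device.

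- Positive = SCD result: specificity 100%.
- Positive = any HbS: every carrier is a false positive. Specificity = 1 − 0.23 / (1 − 0.0239) = 76.4%, and PPV = 0.0239 / 0.2539 = 9.4%.

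The plan expects specificity of 0.97. For an error-free device to show that under the any-HbS rule, carriers could be at most 0.03 × 0.9761 = 2.9% of the children, against the quoted 23%. So the any-HbS rule conflicts with the plan's own table, and the SCD result fits it.

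**3. When is the call made?** Set the Procedure items in order. The chip runs for five minutes and the computer gives a diagnosis. The result is stored and sent to the PI. Caregivers of screen-positive children are telephoned. HPLC specimens travel monthly and their results come back as confirmation. A call is therefore issued and used for each child, ordinarily before that child's HPLC result exists. It is one call per child, which is what the two-by-two formulas take. Plotted on ROC axes, such a call is a single operating point.

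**4. What would tuning cost if it were done?** This is conditional on steps that no passage describes. Assume normal scores, with the SCD group placed so that a fixed cut gives 97% or 98% on both measures, an SCD spread of 1 or 1.5 times that of the others, and a cut chosen to maximise sensitivity plus specificity in the same data. Expected SCD cases: 468 × 0.0239 = 11 and 5,000 × 0.0239 = 120.

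| Setting | 11 cases: reported / true sensitivity of the chosen cut | 120 cases: reported / true |
|---|---|---|
| 97%, equal spread | 99.4 / 92.1 | 97.7 / 96.4 |
| 97%, spread 1.5 | 99.0 / 92.0 | 97.2 / 95.9 |
| 98%, equal spread | 99.8 / 93.2 | 98.6 / 97.4 |
| 98%, spread 1.5 | 99.5 / 93.4 | 98.2 / 97.1 |

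The overstatement is about 6 to 7 points with 11 cases and 1.1 to 1.3 points with 120. In the first setting with 11 cases, specificity is overstated by only about 0.1 point. If the issued diagnosis is the call, no cut is chosen and this overstatement is zero.

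**The case for a change.** The strongest case for a change is that the plan mentions ROC curves at all. A fixed yes/no call gives one point, so the sentence suggests that its authors had a graded reading in mind, and Section 1.3 does mention a quantitative display. Even an issued diagnosis needs a mapping, because the device separates several Hb types, SCD is described as a group of disorders, and the terms for a positive screen and an abnormal HPLC result are undefined. The disease definition in Section 4.4 is only implied, through the prevalence input. A few sentences would settle all of this at no cost in samples or visits.

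Much of this stands as description: the definition is not written down, and the ROC sentence adds nothing to a binary call. It does not show that the planned analysis would go wrong. Section 1.3 is background and describes an optional interface, whereas the Procedure uses a reader and a computer that give a diagnosis. Nothing in the plan calls for choosing a cut against HPLC, and the per-child use of the result makes that the less natural reading. The carrier figures show that the definition matters, but the plan's own table already rules out the reading that would do the damage. As for the Hb types, the documents give no breakdown of SCD by type, so that effect cannot be sized from them. Applying one list to both tests, as any analyst would, avoids a mismatch between the two.

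**Conclusion.** No change to the plan follows. This is an unwritten definition that the rest of the document lets an analyst fill sensibly: the positive call is the SCD diagnosis as the reader issues it, set against SCD on HPLC, with carriers as not SCD. That reading agrees with the sample size of 468, with the expected specificity of 97%, with the two-by-two formulas and with the order of events in the Procedure. Under it, the tuning bias is nil.

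The 6 to 7 points at 468 children (about 1 point at the 5,000 maximum) would arise only with a quantitative score and a cut taken from the same data, neither of which is planned; the size also rests on assumed normal scores and one particular rule for the cut. The 76.4% specificity and 9.4% PPV would arise only under an any-HbS rule that the plan's own figures contradict; they rest on the national prevalence and carrier rate holding in these acutely ill children. The conclusion would differ if the reader gave only a graded reading with no diagnosis, but the Procedure says otherwise.

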6 ETHICAL ISSUES

6.4 Study conduct

The study will be performed in accordance with ethical principles that have their origin in the Declaration of Helsinki and are consistent with the International Conference on Harmonization (ICH)/Good Clinical Practice (GCP).

Informed consent

All study participants must have a legal representative that is in competent mental condition to provide written, informed consent on behalf of the study subject before entering the study. A copy of the signed informed consent form will be given to the parent or legal guardian. Each subject, parent or legal guardian will be notified that they are free to withdraw from the study at any time.

6.5 IRB of record

There will be no research activity performed or data collection at UNMC. All research activity and data collection will be performed at the Nigeria site. The CWRU team will take responsibility for data collection, storage, submitting continuing reviews and

amendments for the study. CWRU team will also give the approved documents to UNMC in a timely manner and make sure to keep track of everything that occurs at that site.

University of Nebraska Medical Center (UNMC) has developed several microbiology diagnostic laboratories for invasive bacterial infections in Nigeria children. UNMC supports the International Foundation Against Infectious Disease (IFAIN), a registered non-profit in Nigeria, which manages local research activities. The Co-I from UNMC, ([name]) is founding member and Trustee of IFAIN and the PI on several grants currently in execution by UNMC through IFAIN in Nigeria. Some of the services IFAIN provides include microbiology and molecular diagnostic services, such as sickle cell disease screening through HPLC. UNMC also has a strong network with multiple researchers across Africa who work with hemoglobinopathies and vaccine preventable infections. UNMC provides essential expertise and support to fulfill the activities for our proposal.

